1.0 Synopsis

Test Article(s) / Prod	 Collagenase Santyl Ointment Bacitracin Ointment 								
Study Dosage / Usag	ly Dosage / Usage:			 Daily application to the burn, approximately 2 mm thick Daily application to the burn, approximately 2 mm thick 					
Active Ingredients:		Collagenase enzymes derived from Clostridium histolyticum							
		2) Baci	tracin antin	nicrobial pep	otides				
Route of Administra	tion:	Topical	1						
Objective(s):		The pri	mary objec	tives are to o	compare the	e proportion of			
		subjects	s healed at	3 weeks afte	r initiation	of Collagenase			
		Santyl	ointment to	Bacitracin o	ointment, in	addition to time to			
		healing	and incide	ence of burn	wound infe	ection between			
		treatment groups. The secondary endpoint is to compare							
		Collage	enage Santy	l ointment v	vith Bacitra	cin ointment based			
		on the s	scar assessr	ment scores a	at 90 days a	after the initiation of			
		treatme	ent. and at 1	80 days afte	r the initiat	ion of treatment.			
		Exploratory endpoints are number of burn wour				n wounds open			
	compared to number of burn wounds closed and cutometer								
		values a	at each scar	rassessment	visit.				
Study Population:		Children and adults $2-75$ years of age, presenting with a							
		minor b	ourn define	d as a partial	thickness l	burn involving			
		< 10%	of the total	body surface	e area (TBS	SA) that does not			
		require	hospitaliza	tion or a ski	n graft.				
Structure:	X Parallel Gro	oup	Duration	of Treatmen	t:	1- 6 weeks			
			Duration	of Assessme	nt:	26 weeks			
	Crossover		N/A						
	Other		N/A						

Blinding:	X	None						
		Observer-Blin	ıd					
		Subject-Blind						
		Double-Blind						
Randomization:	X	Yes Group	p Assignment	Ratio: 1:1				
		No						
Concurrent		No Treatment						
Control:	X	Standard Care	baci	tracin ointment				
		Placebo	N/A					
		Active	N/A	A				
		Other	N/A	A				
Estimated Total S	Sample S	ize: A to	otal of 80 sub	jects will be enrolled with an expectation to				
		con	nplete 80 subj	ects at 90 days after the initiation of treatment.				
Statistical Rationa	ale Provi	ded: X	Yes	Refer to Section 11 for Sample Size				
			No	Justification.				
Variable(s): P	RIMAR	Y:	Proportion h	ealed at 21 days after initiation of treatment,				
			time to heali	ng, and incidence of burn wound infection,).				
S	ECOND	ARY:	Scar appeara	ance (Vancouver Scar Scale) at 90 days and 180				
			days after ini	itiation of treatment				
E	XPLOR	ATORY:	PRY: Burn wound status (open or closed),					
S	AFETY:		Local reaction	ons, adverse events				
P	K:		N/A					
			Refer to Sect	tion 7 for Statistical Design.				

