5. SUBJECTS

5.1 SUBJECT POPULATION

Up to 80 study subjects, aged 2-75 years who meet all study inclusion and exclusion criteria, will be enrolled.

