6. STUDY DESIGN

6.1 STUDY DESIGN

This is an active comparator, parallel group study in which subjects with burns meeting the study criteria will be randomly assigned to outpatient treatment with Santyl or bacitracin in a 1:1 ratio. Subjects who appear eligible will be presented with the study, and consent / assent will be obtained prior to any study procedures being conducted. The safety variables include adverse events and, specifically, burn wound infection or allergic contact dermatitis during treatment. Efficacy variables include time to complete healing and scar appearance. Both the Investigators and the subjects will contribute to these evaluations.

Enrolled, randomized subjects will be prescribed with test article (Santyl or bacitracin) and burn wound dressing supplies sufficient to last until burn wound has healed. Scar assessments will occur at 3 months and 6 months post burn healing.

Recruitment bias will exist, as any subject with a known contact dermatitis to bacitracin will be excluded. This will artificially reduce the number of allergic contact rashes in the bacitracin group, but the effect on the primary endpoint is unlikely to be significant. Study Procedure

For a summary of the required procedures by visit, refer to Table 12: Study Plan.

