6.3 DISCONTINUED SUBJECTS

6.3.1 Definition and Procedures

Discontinued subjects are those who voluntarily discontinue participation, who are withdrawn for safety reasons, or who have missed 2 or more consecutive study visits or 3 or more consecutive test article doses so as to be ineligible for continued study participation. Subjects who discontinue the study prior to completing all of the regularly scheduled visits should complete the visit procedures for the visit at which the subject is being discontinued. If appropriate, the Investigator should also advise the subject of subsequent therapy and/or procedures necessary for their medical condition.

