8. SAMPLE SIZE JUSTIFICATION

A previous study of Santyl vs. white petrolatum in normal volunteers with dermatome wounds enrolled 28 subjects, each of whom served as their own control (paired wounds, treated differently). At 9 months follow-up, the Santyl treated wounds had lower total scores on the Vancouver Scar Scale, suggesting the efficacy of Santyl ointment, although the difference between Santyl and its petrolatum vehicle was not significant (P = 0.09, Wilcoxon signed-rank test).

The current study uses a parallel-group design and non-uniform injuries on different individuals, which are more likely to lead to a larger variance as compared to the previous study. The injuries are non-uniform and different in nature compared to the dermatome study. Assuming a moderate effect size of 0.750 for the present study, the sample size of 80 (40 per group) will yield a statistical power of approximately 70% to detect a difference between the two treatment groups at the significance level of 0.05 (2-sided). Based on a two-sample t-test, the current study is comparable in power to the described previous study.

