9.5 ADVERSE EVENT SEVERITY AND CAUSALITY ASSESSMENT

Events should be classified as mild, moderate, or severe, regardless of whether or not the events are considered to be serious or non-serious. The classification should be based on the following definitions:

- Mild An event is mild if the subject is aware of, but can easily tolerate the sign or symptom
- **Moderate** An event is moderate if the sign or symptom results in discomfort significant enough to cause interference with the subject's usual activities
- Severe An event is severe if the sign or symptom is incapacitating and results in the subject's inability to work or engage in their usual activities

In addition, the Principal Investigator will determine adverse event causality according to the following definitions and with due consideration to conditions and AE normally associated with the population under study:

- **Not Related** An event is considered to be not related to the use of the test article when the event is DEFINITELY UNRELATED or UNLIKELY to have any relationship to the use of the test article.
- Related An event is considered to be related to the use of the test article when there is a
 POSSIBLE, PROBABLE, or DEFINITE relationship between the adverse event and the use of
 the test article.

For example, a single occurrence of an event that is uncommon and known to be strongly associated with drug exposure (e.g., angioedema, hepatic injury, Stevens - Johnson syndrome) has a reasonable possibility of association with the test article. One or more occurrences of an event that is not commonly associated with drug exposure, but is otherwise uncommon in the population exposed to the test article, may have a reasonable possibility of association. Adverse events which are known to be common in the population under study would require additional evidence (e.g., strong temporal relationship, recurrence on re-challenge, unusual severity, and/or increasing frequency) before being considered possibly related.

Adverse events which are known to occur frequently in the population defined by this protocol include: burn wound infection, pain and itch of the burn wound, and contact dermatitis.

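### The synopsis expects all 80 enrolled subjects to complete Day 90, a number the design cannot be expected to deliver, and Section 8 makes no allowance for attrition

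*Combined protocol and SAP*

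**What the plan says.** The sample-size entry in the synopsis (1.0) states that 80 subjects "will be enrolled with an expectation to" complete the same number, 80, at 90 days after the start of treatment. Section 5.1 sets the ceiling: "Up to 80 study subjects, aged 2-75 years who meet all study inclusion and exclusion criteria, will be enrolled". No section mentions replacement, over-enrolment or an attrition rate.

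Section 8 begins "Assuming a moderate effect size of 0.750 for the present study" and attaches a power of about 70% to 40 per group, at a two-sided 0.05 level, by a two-sample t-test. It does not name the endpoint to which the effect size belongs.

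Other sections provide for losses:

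- Section 6.3.1 counts as discontinued those who withdraw, those withdrawn for safety, "or who have missed 2 or more consecutive study visits or 3 or more consecutive test article doses so as to be ineligible".
- Sections 2.2 and 6.2.2 require exit if topical treatment is started for a wound infection. Section 6.2.2 does not require it for systemic antibiotics.
- Section 6.3.2 covers subjects who cannot attend at Day 90 or Day 180. It allows only the subject-rated scar scale to be taken by telephone.

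The secondary endpoint (7.1.2) is the investigator-rated VSS total at Day 90 and Day 180. The synopsis gives no completer number for Day 180.

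**The concern.** A study that can enrol at most 80 reaches 80 completers only if nobody is lost. The protocol asks for daily applications for up to six weeks and treats three consecutive missed doses as grounds for discontinuation. It also sends healed subjects away until Day 90. A subject found healed at Visit 2 (about Day 7) has some 90 - 7 = 83 days without a scheduled visit. Some loss should be expected, and the text plans for it everywhere except in the sample-size entry and Section 8.

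The scar endpoint is the most exposed, because it needs a VSS obtained in person two or three months after most treatment contact has ended, and again at six months. If the number with a VSS falls below 40 per group, the power or detectable difference for that comparison should be quoted at the lower number. The plan gives a reader no means of doing so.

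**Working it through.** **Inputs from the documents.** Enrolled 80 and expected completers 80 (1.0); ceiling 80 (5.1); allocation 1:1 (6.1), so 40 per group; effect size d = 0.750, alpha 0.05 two-sided, two-sample t-test, power about 70% (8). No loss rate is given, so every loss rate below is an assumption.

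**1. The plan's own figure.** With n per group, the noncentrality is d × √(n/2) on 2n - 2 degrees of freedom.

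- n = 40: 0.750 × √20 = 3.354. The normal approximation gives Φ(3.354 - 1.960) = Φ(1.394) = 91.8%; the noncentral t gives 91.2%.
- The stated 70% is not reproduced. Other readings do not reach it either: one-sided 95.4%, alpha halved 85.5%, alpha divided by three 81.5%, 20 per group 63.7% (all noncentral t).
- At d = 0.750, 70% power needs about 23 per group. At 40 per group, 70% power corresponds to d of about 0.56.

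**2. How likely 80 of 80 is.** With independent loss q per subject, the chance that all complete is (1 - q)^80.

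| Assumed loss per subject | Chance that all 80 complete |
|---|---|
| 1% | 45% |
| 2% | 0.98^80 = 20% |
| 5% | 0.95^80 = 1.7% |
| 10% | 0.02% |

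**3. Effect of loss on a two-group comparison of means.** Completers are 80 × (1 - loss), and the standard error grows by 1/√(1 - loss).

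| Assumed loss | Completers (per group) | Standard error | Power at d = 0.750 | Power at d ≈ 0.56 | Effect detectable with 70% power |
|---|---|---|---|---|---|
| 0% | 80 (40) | 1.00 | 91.2% | 70.0% | 0.56 |
| 10% | 72 (36) | 1.05 | 88.1% | 65.3% | 0.59 |
| 20% | 64 (32) | 1.12 | 84.0% | 60.1% | 0.63 |

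At d = 0.750, power falls to 70% only at about 46 completers: 1 - 46/80 = 42.5%, or about 43% loss.

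**4. Can a lost VSS be recovered?**

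- The telephone route (6.3.2) covers only the subject's scale.
- Last observation carried forward (7.1) is written for weekly visits, while the Section 12 table schedules the VSS only at Visits 7-8.
- A discontinuing subject completes the procedures of that visit (6.3.1), and under the table an exit at Visits 2-6 yields no VSS. Section 7.1.2 lists Visits 5 and 6 as model time points, but neither the table nor 6.2.2 schedules a VSS there.
- Under 6.5.5 the VSS begins only once the wound has re-epithelialized, so an exit with an open wound has none.
- The rule in 7.1.2 moving an early-termination VSS to the next scheduled visit helps only those who have such a score.

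**The case against.** A reader might infer that attrition leaves the trial below its stated power, or that the plan overstates the precision of the scar comparison. The documents support neither. No confidence-interval width or other precision is given for the scar endpoint. Section 8 mentions the VSS only for the earlier dermatome-wound study and does not tie 0.750 to it. At the stated inputs, power exceeds 70% even after a 20% loss. A shortfall appears only if 70% is the intended figure and 0.750 is not, and the text does not settle that.

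Four further points weigh on the other side:

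- The absence of a replacement rule is silence, not a prohibition.
- Section 9.5 says "Adverse events which are known to occur frequently in the population defined by this protocol include: burn wound infection", but infection is not the same as exit. Only topical treatment triggers discontinuation, and no rate for it is given.
- The primary endpoints are healing and infection. Sections 7.1 and 7.1.1 already analyse them in all randomised subjects, so that denominator needs no correction.
- Some discontinued subjects can supply a VSS through the early-termination rule.

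All of this stands, and it limits the consequence. It does not rescue the completer number: with a ceiling of 80 and no stated replacement, one loss makes 80 completers unattainable, and the recovery routes miss most early exits.

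**Conclusion.** The expectation of 80 completers at Day 90 has no stated basis and conflicts with the protocol's own provisions for discontinuation and missed visits. Section 8 uses the full enrolled number without an attrition allowance.

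The size of the effect depends on assumed loss. At 10-20%, 72 to 64 subjects would have a VSS and the standard error would rise by 5-12%. The cost in power is 3 to 7 percentage points if 0.750 is right (91% to 88-84%), or 5 to 10 points if 70% is right (70% to about 65-60%). These figures assume equal loss in both groups, a t-test on completers, and no score recovered for those lost.

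The gap between the stated 70% and the 91% that its inputs give, about 21 points, is larger than the attrition effect. It has to be settled first, because until then nobody can say which power column applies.

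**What to change.** 1. In the synopsis, keep enrolment at 80. Replace the expectation of 80 completers with the expected number having a VSS at Day 90 and, separately, at Day 180, under a stated loss assumption. As an illustration, 10-20% loss gives 72-64 in total.
2. In Section 8, name the endpoint and reconcile effect size 0.750, 40 per group and 70% power. Then restate power or the detectable difference at the expected number per group: for 36-32 per group, 88-84% at 0.750, or a detectable effect of 0.59-0.63 at 70% power.
3. State whichever replacement rule applies. The choice is the sponsor's.

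The cost is wording in the synopsis, Section 5.1 and Section 8. It adds no subjects or visits and changes no clinical rule. The quoted power may move either way: up from 70% if 0.750 is confirmed, down if 70% was intended at 40 per group.

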1.1 LIST OF ABBREVIATIONS AND DEFINITIONS OF TERMS

Abbreviation	Definition
ADR	Adverse Drug Reaction(s)
AE	Adverse Event(s)
ANCOVA	Analysis of Covariance
ANOVA	Analysis of Variance
AST/SGOT	Aspartate Transaminase
CIB	Clinical Investigator's Brochure
cm ²	Centimeters squared or square centimeters (area)
eCRF	electronic Case Report Form
FDA	Food and Drug Administration
GCP	Good Clinical Practice
IEC	Independent Ethics Committee
IRB	Institutional Review Board
ITT	Intent-to-Treat
LOCF	Last Observation Carried Forward
μg	Microgram
m^2	Meters squared or square meters (area)
N	Sample Size
N/A	Not Applicable
NDA	New Drug Application
QD	Once Daily
SAE	Serious Adverse Event(s)
SAS	Statistical Analysis Software, SAS® Institute, Cary, NC
TBSA	Total Body Surface Area
TM	Trademark
UPT	Urine Pregnancy Test

2. INTRODUCTION

2.1 BACKGROUND

Burns are injuries caused by heat, electricity, chemicals, radiation, or light (1). In the US about 450,000 people per year receive medical burn care through hospital emergency departments, hospital outpatient clinics, free-standing urgent care centers and private physician offices (2). Most burns only affect the epidermal and dermal tissues, but more severe burns can also involve muscle, bone, tendons and blood vessels. Burns are generally classified in terms of depth and severity. First degree burns are superficial, involve the epidermis only, and will heal spontaneously within a week or less. Second degree (partial thickness) burns extend into the dermis, are characterized by blisters, and may take up to several weeks to heal. Second degree burns can also become infected, and result in scarring and/or contractures which may require excision and skin grafting. Burns that extend through the entire dermal layer are classified as third degree burns. These burns require excision and in addition to scarring and contractures, may result in amputations.

The American Burn association has further classified burns as minor, moderate, or major depending on several factors including total body surface area (TBSA) burned, involvement of specific anatomical zones, the age of the person, and associated injuries (3). Briefly, moderate and major burns generally require hospitalization, while minor burns do not. A minor burn is one that is partial thickness involving < 15% TBSA for persons 10 to 50 years of age, or is a partial thickness burn involving < 10% TBSA for individuals younger than 10 or older than 50 years of age.

Collagenase Santyl[®] Ointment was approved by the FDA in 1965 and is currently distributed by Smith and Nephew as an enzymatic debriding agent indicated for use on chronic dermal ulcers and severely burned tissue (4,5). Santyl is a sterile and anhydrous product formulated in a white petrolatum base. The product contains a mixture of enzymes, most prominently collagenases that effectively attack human fibrillar collagen both from the end and the middle of the triple-helix molecule.

Collagenase enzymes are uniquely able to cleave intact collagen, thereby freeing devitalized tissue on the wound surface from its granulation base. Although collagenase is understood to act by cleaving native collagen, it has been observed that Santyl does not impede wound healing or otherwise damage healthy granulation tissue. The explanation for this is unknown. Candidate hypotheses include actions by tissue inhibitors occurring only in healthy granulation tissue, or a strictly kinetic mismatch between rates of tissue collagen production and rates of proteolysis by topical collagenases.

In addition to its safety and effectiveness in debriding the wound surface, Santyl has been reported to promote wound healing. The mechanism by which this might occur is likely to be complex, with various lines of evidence suggesting that additional mechanisms are at work beyond debridement. Observations of improved healing in patients treated with Santyl correlated with improved healing in animal burn models according to work by Zimmerman in the 1970s (6). By contrast, pancreatic enzyme preparations (Tripure Novo, Pancrazym-N) and another bacterial enzyme preparation (Fibrolan, Pfizer, Inc.) showed debridement without healing. Later studies comparing Santyl to Silvadene® Ointment in burn victims suggested both a faster rate of healing with the collagenase preparation (7,8) and a decrease in the incidence of hypertrophic scarring (9).

In the early 1990's, Saarialho-Kere and colleagues recognized that basal keratinocytes at the edge of a cutaneous wound express matrix metalloproteinase-1 (MMP-1), also known as interstitial collagenase (10). Their findings were confirmed by others (11), and more recently it has been found that non-healing wounds are marked by a lack of MMP-1 expression by leading edge keratinocytes (12). As reported by Riley (13), keratinocytes plated on biosynthesized matrices showed a 2-fold increase in proliferation and post-injury migration in the presence of clostridial collagenase. When this collagenase was added to the growth media, there was an additional doubling of growth and migration, yielding approximately 5-fold enhancement of keratinocyte proliferation and migration overall. In the same report, Riley noted that a double-blind study of full-thickness wounds on the backs of Yucatan micro pigs showed that purified clostridial collagenase improved wound healing by all parameters measured, including granulation tissue formation, inflammation, re-epithelialization, and time to wound closure. Thus clostridial collagenase has been found to affect the interaction between keratinocytes and matrix both *in vitro* and *in vivo*. Another intriguing potential mechanism *in vivo* may be the attraction of M2-type macrophages by collagen type-1 fragments (14).

The use of Collagenase Santyl Ointment for treatment of burn injuries was well described in 1972 by Zimmerman, who noted that good results were obtained in terms of both healing and reduced scarring (6). More than 30 years later, the observation of decreased incidence of hypertrophic scars following use of Collagenase Santyl Ointment on burn wounds has again been published (9). Santyl has been used in combination with antibiotics for burn wounds with good results (7), and animal studies indicate that it may be used safely without antibiotics in experimental wounds contaminated with E. coli (15). Given the continuing, if not growing desirability of a pharmacologic agent which reduces scar formation or

improves the appearance of scars (16), this clinical study has been designed to prospectively evaluate potential benefits of Santyl in partial thickness burn wounds compared to antibiotic only treatment.

A summary of known and potential risks and benefits to humans of the test articles can be found in the Package Inserts for Collagenase Santyl Ointment and bacitracin ointment.

2.2 RATIONALE

Outpatient management of partial thickness burns normally involves the application of an ointment, which may contain an antibiotic. Concerns about the promotion of antibiotic resistant staphylococci, combined with known risks of allergic hypersensitivity reactions to certain topical antibiotics, support the exploration of alternative treatments. Bacitracin ointment has been compared against white petrolatum in the management of post-procedural wounds among 922 patients with 1249 wounds (17). No significant difference was observed in infection rates (2% in the petrolatum group vs. 0.9% in the bacitracin group) or healing rates. No patients in the white petrolatum group developed allergic contact dermatitis compared with 4 patients (0.9%) in the bacitracin group. In a separate study of 142 patients, 147 Mohs micrographic surgery wounds on the ear were postoperatively treated with either gentamicin ointment or petrolatum. No significant differences were seen between treatments in the incidence of suppurative chondritis infections (4.76% in the gentamicin group; 6.67% in the petrolatum group), whereas there was a higher incidence of inflammatory chondritis in the gentamicin group (11.90% vs. 3.33% for petrolatum) (18). In the 1990s, the North American Contact Dermatitis Group (NACDG) listed bacitracin among the top 10 allergens, based on skin testing. Approximately 9% of bacitracin tests were positive.

. Bacitracin ointment is selected for this study because it is a standard treatment used by the Investigators, and is widely used in burn care. A significant cost difference exists between bacitracin and other ointments, such as Collagenase Santyl. The therapeutic intent for this study is to see if there is a cost reduction benefit as well as reduction in healing time for two standard of care treatment options for partial thickness burn wounds.

This trial does not include a rigorous evaluation of local infection, as quantitative bacteriology from biopsied tissue would be required, nor does it include a rigorous evaluation of hypersensitivity reactions, as de-challenge / re-challenge or measurement of specific humoral and cellular immune responses would be required. Instead, the appearance of the wound bed and periwound tissue will be evaluated, with

particular attention to the description of any rashes. Clinically diagnosed infections may be treated, but use of topical treatment will require that the subject exit the trial.

